Based on audits of our *Registry* data, we expect <1% missing data for the following key elements: institution, sex, ethnicity, gestational age at birth, delivery mode, Apgar scores, hypothermia treatment, indication for EEG, seizure type, primary seizure etiology, disposition and seizure medication prescribed at the time of discharge. For Aims 1 and 3, in our study design we have conservatively accounted for 15% loss to follow-up (the anticipated main source of missing data) and have adjusted our enrollment target accordingly. We will perform sensitivity analyses to assess the potential impact of loss to follow-up: we have extensive information about our participants and will compare those that are and are not lost to follow-up. We will compare our primary analysis (a complete case analysis) with an analysis using multiple imputation using the "multiple imputation with chained equations" methodology. This approach allows us to specify realistic models for each variable, such as the ordered categorical for the Engel scale. For Aim 2, we expect little to no missing data. Also, for Aim 3, we will audit the amount of missing data for the open-ended free-text questions to determine if there are patterns and will consult with our Parent Partners about ways to improve response rates if needed.

Heterogeneity of treatment effects [HT-1 to 4]. As suggested by PCORI methodological guidelines, all assessments of heterogeneity of the effect of short versus prolonged phenobarbital treatment have been preplanned and have been justified (see *Potential participant subgroups* section below). Analysis will be by entering subgroup by intervention interaction effects in the analyses described above to test for moderation.

Reporting plan [IR-6]. Data will be reported according to STROBE (Strengthening the Reporting of Observational studies in Epidemiology) guidelines, as is recommended for observational studies.

Patient-centered outcomes research (PCOR) data registry details are presented in Appendix 6.

D. Project Milestones and Timeline

Table 3: Project Timeline

	Months					
	1-6	7-12	13-18	19-24	25-30	31-36
Planning						
- Finalize protocol	\checkmark					
- IRB approval	\checkmark					
 Clinicaltrials.gov registration & results reporting 	~					\checkmark
Patient Enrollment						
- Start recruitment		\checkmark				
- Complete 25% recruitment		\checkmark				
- Complete 50% recruitment			✓			
- Complete 75% recruitment			✓			
- Complete enrollment				~		

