Appendix 4: Seizure/Epilepsy Follow-Up Telephone Questionnaire (Aim 1b)

Date	
Subject #	Subject age
Person completing questionnaire	

- 1. Did your child have seizures as a newborn (at any time during the first 28 days of life)?
 - a. Yes
 - b. No
 - c. Don't know
- 2. If your child was treated with medicine for neonatal seizures, did he/she ever stop taking this medicine?
 - a. Yes, before we left the hospital
 - b. Yes, after we left the hospital
 - c. No
 - d. Don't know
- 3. Your child was treated in the hospital for his or her seizures. After you went home from that admission, did your child ever have more seizures?
 - a. Yes
 - b. No
 - c. Don't know

[If answer to 3. Is "No", then indicate answer "a" for question 5 and end telephone survey. If yes, then continue.]

- 4. Let's talk about the seizure that happened after you went home from the hospital. When did your child start having seizures?
 - a. Age_____ months
 - b. Don't know
- 5. How often does your child have a seizure now?
 - a. No seizures since he/she was a newborn
 - b. Seizure-free for at least 6 months (# of months seizure-free _____)
 - c. 1 12 seizures per year (Fewer than 1 seizure per month)
 - d. 1-4 seizures per month
 - e. 5-30 seizures per month
 - f. >30 seizures per month (daily seizures)
 - g. Multiple seizures a day (2 or more seizures per day)
 - h. Don't know
- 6. Has your child ever been diagnosed with infantile spasms (a particular kind of epilepsy)?
 - a. Yes
 - b. No
 - c. Don't know
- 7. Is your child taking medication for seizures now?
 - a. Yes (Name of medication(s), if known _____
 - b. No
 - c. Don't know

Epilepsy questions for medical record review:

- 1. Did the child remain seizure-free after discharge from the admission during which neonatal seizures were diagnosed?
 - a. Yes.
 - b. No. Acute symptomatic neonatal seizures stopped, but unprovoked seizures began later.
 i. Date of first unprovoked seizure:
 - c. No. Seizures persisted without a convalescent period.
 - d. Don't know.

2. Postneonatal seizure semiology:

- a. No seizures
- b. Seizure semiology:

	no	Yes, not specified	Bilateral, symmetric	Bilateral, asymmetric	Unilateral, focal	Unilateral, Hemi
Epileptic spasms						
Tonic						
Clonic						
Tonic Clonic						
Myoclonic-Tonic						
Myoclonic						
Myoclonic-Atonic						
Absence						
Atonic/Drop-attack						
Arrest/Staring/Blinking seizures						
Other Focal Motor						
Sensory/Autonomic						

- 3. Date of postneonatal epilepsy diagnosis:

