Appendix 6: Standards for Data Registries [DR-1 to DR-3]

Patient Follow-up will be at pre-specified ages as outlined in the proposal. The initial follow-up (2-4 month EEG) will be arranged at the time of enrollment for the N=150 prospectively enrolled infants. The Aim1 12-month, 18-month, and 24-month follow-up assessments for all participants will be conducted by telephone and will include:

- WIDEA FS (functional neurodevelopmental outcome, which is the primary endpoint, Appendix 3)
- Epilepsy assessment (Appendix 4)

As requested by our Parent Partner Advisory Panel, participating families may complete 12-month follow-up family wellbeing assessment for Aim 3 either by mail (paper copies of the questionnaires) or via online questionnaire administration (**Appendix 5**).

The 24-month contact is planned to be the last contact with patients and their families.

Adequacy of Follow-Up Duration: 24-month follow-up is both scientifically justified and practical. By 12 months, those with significant developmental delays can be identified using standard neurodevelopmental assessment instruments, such as the WIDEA FS. Additionally, those with the most severe forms of post-neonatal epilepsy, such as infantile spasms, typically present before the child's first birthday. Although more subtle developmental differences may emerge later, in school age children, longer follow-up is not feasible within a 3-year grant cycle. We plan to request permission from enrolled families to contact them at a later date for long-term outcome assessment, once additional funding is secured.

Retention and Expected Loss to Follow-Up: We anticipate excellent retention, since all neonates enrolled in this study will have close clinical follow-up with the study centers through a high-risk developmental follow-up program, pediatric neurology, and/or pediatric epilepsy. We have designed the protocol to avoid unnecessary travel to the study centers. The follow-up EEG will be recorded between ages 2 and 4 months, a timeframe during which typical neurology clinical assessments are scheduled. The assessments will be conducted via telephone interview (Aim 1), and online or by mail (Aim 3), rather than in-person evaluations. Despite this, we have accounted for a 15% loss to follow-up in our analysis plan.

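### The seizure-frequency question behind the epilepsy severity score has no answer for a child whose frequent seizures stopped less than 6 months ago

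*Combined protocol and SAP*

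**What the plan says.** The Aim 1 approach in Specific Aims uses a questionnaire to define epilepsy incidence and a modified Engel classification for its severity, assessed at 12, 18 and 24 months. Scales and tests [IR-4] derives the Engel class from the survey questions together with chart review. Missing data [MD-1 to 5] intends a multiple-imputation model that respects the type of each variable, "such as the ordered categorical for the Engel scale".

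The frequency information comes from Appendix 4, item 5: "How often does your child have a seizure now". The answers are:

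- **a:** "No seizures since he/she was a newborn". The skip rule fills this in when item 3 (any seizure after going home) is answered no.
- **b:** "Seizure-free for at least 6 months", with a blank for the number of months.
- **c:** 1 to 12 a year, glossed in brackets as under one a month.
- **d:** 1 to 4 a month.
- **e:** 5 to 30 a month.
- **f:** ">30 seizures per month (daily seizures").
- **g:** "Multiple seizures a day (2 or more seizures per day").
- **h:** don't know.

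The chart-review part of Appendix 4 asks for the seizure course after discharge, the date of the first unprovoked seizure, semiology, epilepsy diagnosis and its date, and treatments.

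**The concern.** An ordered severity scale needs answers that cover every child and place each child once. Item 5 leaves out children in recent remission after frequent seizures. The likely entries for such a child are code h, which amounts to missing, or one of codes c to g, which places a controlled child with children still having seizures.

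The omission falls where the plan expects cases. Appendix 6 says that the most severe post-neonatal epilepsies, "such as infantile spasms, typically present before the child's first birthday". A child with onset in the second half of the first year is therefore likely to be active or only recently controlled at the 12-month call. The severity comparison between short and prolonged treatment, and any imputation of the Engel class, would carry that misplacement.

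**Working it through.** The plan states no figure to reproduce, so the check takes each answer literally and asks which children satisfy it.

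**The gap.** Take a child who has had post-discharge seizures, has none now, and has been seizure-free for F months.

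- Code a is false, because there were seizures after the newborn period.
- Code b needs F ≥ 6. With F of 1, 3 or 5.9 months, b is false. At F = 6 it becomes true.
- Codes d to g describe a current rate of at least one a month. The current rate is 0, so all are false.
- Code c is also false on current rate. Read as a look-back over the past year, it could fit a child with a few seizures in that year. It cannot fit a child with more than 12.

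Example: frequent spasms from 7 to 8 months of age and none since. At the 12-month call F = 12 − 8 = 4, so b fails, and the earlier frequency rules out c. No answer from a to g applies.

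**When code b can be reached.** The latest age at last seizure that allows code b is the age at the call minus 6 months:

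| Call | Latest age at last seizure for code b |
|---|---|
| 12 months | 12 − 6 = 6 months |
| 18 months | 18 − 6 = 12 months |
| 24 months | 24 − 6 = 18 months |

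A child whose first post-discharge seizure came after 6 months of age therefore cannot be coded b at the 12-month call.

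**Whether another field closes the gap.** The months-free blank belongs to code b, so a shorter remission is not recorded. The chart-review items give the first seizure and the diagnosis date, but not the last seizure or the current frequency.

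**The overlaps.**

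- Top: 2 a day × 30 days = 60 a month, which exceeds 30. Code f has no upper limit, so every child in g also meets f. Only rates above 30 and below about 60 a month belong to f alone.
- Bottom: 12 a year ÷ 12 = 1 a month. This meets c by its count and d by its lower limit, and conflicts with c's own gloss. It is a single boundary value.

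**Possible size.** The documents give no remission data, so these are assumptions: onset uniform from 2 to 18 months of age, 40–70% of cases controlled, and an exponential time from onset to last seizure with a mean of 2 or 4 months. The simulated share is the number of controlled cases with 1 ≤ F < 6, divided by cases with onset before the call.

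| Call | Share of existing cases |
|---|---|
| 12 months | 16–33% |
| 18 months | 12–22% |
| 24 months | 5–12% |

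The plan's 20% epilepsy incidence gives 0.20 × 300 = 60 cases, or 0.20 × (0.85 × 300) = 51 after its 15% loss to follow-up. At 24 months, 4.6–12.2% of 60 is about 3–7 children, and of 51 about 2–6. These are upper bounds, because the simulation counts every recently controlled child, including those with infrequent seizures who could be placed in c.

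**The case against.** The strongest case on the other side is that this is a small gap in a secondary descriptive measure. Its parts are taken in turn.

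- **Infrequent seizures fit code c.** A child with three seizures in the past year, the last 3 months ago, can reasonably be placed there, and requiring 6 months before counting remission is a defensible choice. This stands, and it confines the gap to children whose seizures were more frequent than c allows.
- **The item is asked again.** A child uncoded at 12 months who stays controlled becomes code b at 18 months, with the months recorded. This stands, and it allows some later correction. It does not help a child whose frequent seizures stopped after 18 months of age, because 24 months is the last planned contact.
- **The Engel class also uses chart review, and a rule may exist elsewhere.** Appendix 6 places standard instructions in the Manual of Operations, which is not among the documents. A rule there cannot be excluded. The chart-review form that is shown has no field that would supply the missing information.
- **The overlaps have an evident intent.** Code f's gloss suggests roughly daily seizures and g two or more a day, while c's gloss sends 12 a year to d. This largely stands. The overlaps need tidying, but they are not what misplaces recently controlled children.

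A reader might also infer that the per-year count in c is ambiguous for a child with under a year of seizures, such as 8 seizures in 4 months. The documents do not support this: 8 ÷ 4 = 2 a month, which c's gloss excludes and d includes.

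**Conclusion.** The defect holds on the wording of Appendix 4, and it is minor. A child with previously frequent post-discharge seizures who has been seizure-free for under 6 months has no valid answer to item 5. The form as written makes that child missing or actively seizing. The overlap of f with g and the shared value of c and d are lesser faults of drafting.

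Only the severity measure is affected. A reader might infer that the Aim 1b comparison of epilepsy incidence, with its 13% margin, is compromised. It is not: incidence rests on item 3 and the chart-review diagnosis. The primary WIDEA FS outcome is also untouched, and severity has no stated hypothesis, margin or power.

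A reader might also take the simulated shares as estimates, and conclude that up to a third of cases are lost at 12 months. The documents do not support that. The onset, control and remission inputs are assumptions, and the shares are upper bounds. The logical gap does not depend on them. The effect on the Engel class itself is inferred, because the documents give no mapping from item 5 to the classes.

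**What to change.** 1. For every child with item 3 answered yes, record the date of the last seizure, or the months since it, as a separate field.
2. Add a code for no current seizures with a seizure-free interval under 6 months. State that it takes precedence over c to g only when that interval is clearly longer than the child's usual interval between seizures, and define clearly longer in the Manual of Operations. Without such a rule, a child with a seizure every two months and the last one six weeks ago would meet both the new code and c.
3. Reword c as at least 1 but fewer than 12 a year, and f as more than 30 a month but fewer than 2 a day.
4. State how each code maps to the modified Engel class.

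The cost is a small change to one form and its REDCap fields. Forms already completed can be recoded only in part, from the medical record and from later calls, because the months-free blank was not open to the children concerned.

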Appendix 5: Parent and Family well-being scales (Aim 3)

Domains of well-being	Questionnaire	Timepoints	Rationale
Parent quality of life	WHO-Brief QOL	NICU Discharge & 12, 18, &	The most comprehensive
		24 months	and yet brief; well-validated
Parent anxiety and	HADS	NICU Discharge & 12, 18, &	The most comprehensive
depression		24 months	and yet brief of the surveys
			reviewed; well-validated
Family coping	Impact on	NICU Discharge & 12, 18, &	Have been used with
	Family;	24 months	families of children with
	Understanding		epilepsy as well as many
	the medical		other conditions
	situation		
	subscale of		
	Coping Health		
	Inventory for		
	Parents		
Parent post-traumatic	Impact of events	12, 18, & 24 months	One of the most well-known
stress			measures of post-traumatic
			stress symptoms in relation
	.		to a specific event
Parent post-traumatic	Post-traumatic	12, 18, & 24 months	Allows us to examine
growth	growth		positive and negative
			outcomes after a stressful
Darant/infant/family	Study coocific	NICLI Discharge & 12, 19, 8	These variables are needed
	instrument with	74 months	to describe the sample and
socio-demographics	standard items		may be adjusted for if they
	(education		have an independent effect
	employment		on the outcomes of interest
	etc) and narent		on the outcomes of interest
	report of infant		
	condition and		
	treatment		
Open-ended guestions	Study specific	NICU Discharge & 12, 18, &	These guestions will be
	instrument to	24 months	asked as part of the surveys,
	explore in more		and will also be used as a
	depth the effects		question guide to engage a
	of the seizures		subset of parents in a more
	and treatment		in depth interview to
	on parent, child		describe their experiences
	and family well-		and perceptions
	being		

PCORI Research Plan Template Version 2-8/1/2016

PRINCIPAL INVESTIGATOR: [name]

Open-ended questions to be answered by a parent at the time of hospital discharge:

Date_____

Subject # _____

Ethnicity:_____

Race: _____

1. What level of agreement or doubt was there among the medical care team about the duration of anti-seizure medication treatment? How did that make you feel? How did it impact your family?

2. On a scale of 1 to 5, with 1 being not confident at all and 5 being very confident, how confident do you feel about taking care of your baby's medical condition?

3. Will your child's treatment affect your usual family routines (Yes or No)? If so, how?

- 4. In what other ways might your child's treatment impact you and your family?
- 5. The most positive part of caring for my child is:

6. The most difficult part of caring for my child is:

7. Do you have any worries/concerns/fears about your child's seizure condition or treatment (Yes or No)? If yes, please describe.

Open-ended questions to be answered by a parent at the 12-month follow-up:

Date_____

Subject # _____

Ethnicity:

Race: _____

1. Looking back, what if any, impact did your child's seizure medication during the NICU stay have on you or your family? If your child continued to receive medication for seizures in the past year, what if any impact did this treatment have on you or your family? How did affect your usual family routines?

2. Looking back at the time of discharge from the NICU, what questions did you have about your baby's condition at the time of discharge? What recommendations do you have for other parents in the same situation? What recommendations do you have for the clinical staff?

3. Looking back over the past year of caring for your baby, what questions did you have about your baby's condition at the time of discharge? What recommendations do you have for other parents in the same situation? What recommendations do you have for the clinical staff?

4. Looking back, what level of agreement or doubt was there among the medical care team about the duration of antiseizure medication treatment? How did that make you feel? How did it impact your family?

- 5. The most positive part of caring for my child is:
- 6. The most difficult part of caring for my child is:

7. Do you have any worries/concerns/fears about your child's seizure condition or treatment? (Yes/No) If yes, please describe:

Appendix 6: Standards for Data Registries [DR-1 to DR-3]

Patient Follow-up will be at pre-specified ages as outlined in the proposal. The initial follow-up (2-4 month EEG) will be arranged at the time of enrollment for the N=150 prospectively enrolled infants. The Aim1 12-month, 18-month, and 24-month follow-up assessments for all participants will be conducted by telephone and will include:

- WIDEA FS (functional neurodevelopmental outcome, which is the primary endpoint, Appendix 3)
- Epilepsy assessment (Appendix 4)

As requested by our Parent Partner Advisory Panel, participating families may complete 12-month follow-up family wellbeing assessment for Aim 3 either by mail (paper copies of the questionnaires) or via online questionnaire administration (**Appendix 5**).

The 24-month contact is planned to be the last contact with patients and their families.

Adequacy of Follow-Up Duration: 24-month follow-up is both scientifically justified and practical. By 12 months, those with significant developmental delays can be identified using standard neurodevelopmental assessment instruments, such as the WIDEA FS. Additionally, those with the most severe forms of post-neonatal epilepsy, such as infantile spasms, typically present before the child's first birthday. Although more subtle developmental differences may emerge later, in school age children, longer follow-up is not feasible within a 3-year grant cycle. We plan to request permission from enrolled families to contact them at a later date for long-term outcome assessment, once additional funding is secured.

Retention and Expected Loss to Follow-Up: We anticipate excellent retention, since all neonates enrolled in this study will have close clinical follow-up with the study centers through a high-risk developmental follow-up program, pediatric neurology, and/or pediatric epilepsy. We have designed the protocol to avoid unnecessary travel to the study centers. The follow-up EEG will be recorded between ages 2 and 4 months, a timeframe during which typical neurology clinical assessments are scheduled. The assessments will be conducted via telephone interview (Aim 1), and online or by mail (Aim 3), rather than in-person evaluations. Despite this, we have accounted for a 15% loss to follow-up in our analysis plan.

Possible biases due to differential loss to follow-up: It is possible that infants who are discharged from the initial hospital admission *without* anticonvulsant medication will be more likely to be lost to follow-up, since they will not need to present to a neurology clinic for prescription medication refills. In our clinical experience, however, these families want to return to clinic at least at the 2-4 month time point, so that a specialist can evaluate their child's growth and development. If a child is doing well, families who live farther from the study site may be less likely to follow-up at later time points. We have designed the assessment to avoid this problem by utilizing telephone interviews, online and mailed surveys. Even for families who do not complete the assessments, the medical chart can be reviewed. In cases where a family cannot be reached by telephone, a diagnosis of epilepsy will be readily apparent from electronic medical record review.

Data Safety and Security: Local Institutional Review Boards approvals for the *Neonatal Seizure Registry Sites* will be amended to reflect changes to the study design. Data will be collected using REDCap, an online, HIPAA compliant database that is designed for use in health care. Data will be de-identified, with each site maintaining local record of the patient medical record number in a secure manner (either on an encrypted and password protected computer that is maintained in a locked room, or paper file that is maintained in a locked cabinet in a locked room). Data that were collected for the *Neonatal Seizure Registry* prior to initiation of this proposal will be used only following informed consent from families.

Informed Consent: A study investigator will contact the parents/legal guardians of eligible patients and, using a consent form approved by the local Committee on Human Research (Institutional Review Board), describe the known risks and benefits of the study. The consent teams will include only experienced study personnel who are sensitive to the vulnerable nature of this population and who will emphasize the voluntary nature of research.

Data Quality Assurance

Data will be collected and entered into a REDCap database according to policies established for the *Neonatal Seizure Registry*.

Training: For the purposes of this proposal, the two study coordinators from the primary institutions will provide additional training for coordinators at the other study sites. For the purposes of the *Neonatal Seizure Registry*, we have audited 100% of sites and have found very good agreement for the variables that will be included in the proposed analysis. We expect a similar high fidelity for additional data collection.

Data Accuracy and Editing: The database limits range values for numerical data and will utilize radio buttons or drop down lists rather than free text for qualitative data.

Updating: REDCap automatically creates a historical record of past saved data for each field so that errors can be traced. Data and Form Checks: Database quality is maintained through analyses that target anomalies, delinquent data, and data entry errors. Along with built-in data validation, the Study Coordinator performs a quarterly check for discrepancies in data that includes: incorrect data types, out-of-range or erroneous data, inconsistent and illogical over-time dates, fields on a "completed form" actually not completed; or no reason for missing data is provided. Sites are notified of data discrepancies and are asked to verify and correct discrepancies within 2 weeks of notification.

Data Review and Verification Procedures: Database quality will be maintained through analyses that target anomalies, delinquent data, and data entry errors. Along with built-in data validation, the Study Coordinators will perform a quarterly check for discrepancies in data that includes: incorrect data types, out-of-range or erroneous data, inconsistent and illogical over-time dates, fields on a "completed form" actually not completed; or no reason for missing data is provided. Sites will be notified of data discrepancies and are asked to verify and correct discrepancies within 2 weeks of notification.

Modifications to the Protocol will be based on consensus of the co-Pis after discussion with Parent Partner Advisory Panel. Any changes will trigger an update to the Manual of Operations, which will be sent electronically to every site PI and study coordinator. Changes will be highlighted during conference calls and the main study coordinators will communicate directly with each site coordinator to insure timely and accurate implementation of any change.

Consistent Data Collection: We will use the existing data dictionary for the *Neonatal Seizure Registry*, which is based on recent literature review and widely used definitions. Standard instructions and definitions are included in the Manual of Operations.

Systematic Patient Enrollment and Follow-up: Every infant diagnosed with neonatal seizures at the participating centers will be a potential candidate for enrollment. Only families whose infants survive to hospital discharge will be approached for consent (~16% in-hospital acute mortality among those already enrolled in the *Neonatal Seizure Registry*). This will avoid selection bias and allow for the most widely applicable data set. Each site will maintain a log of families who decline to consent for this study. The log will include gender, race/ethnicity, and the reason for the neonatal seizures (these data are already gathered through the *Neonatal Seizure Registry*). This will allow for prospective identification of any biases in enrollment, so that changes in the consent process may be implemented as needed to enhance generalizability of the study sample.

Procedures to Monitor and Minimize Loss to Follow-up: Quarterly enrollment and follow-up reports will be generated for each site, so that the follow-up rates are clear and any center for which the target appears to be in jeopardy can be readily identified before the follow-up target is missed. The target is >85% follow-up for the 24-month assessments. We will prospectively determine the actions to be employed in the event that this target is in jeopardy. At the outset of the study, we will develop a patient retention plan that documents when a patient will be considered lost to follow-up and what actions will be taken to minimize such loss.

- At the time of enrollment, the following data will be collected: Telephone, mailing address, and email address for the neonate's parent/legal guardian, as well as alternate contact information for that parent/guardian (e.g. a grandparent or close friend's contact information, with that person's permission).
- The 2-4 month follow-up EEG will be planned and scheduled at the time of study enrollment, with every effort made to coordinate that appointment with another clinically-indicated appointment (*e.g.*, the pediatric neurology follow-up clinic visit). This will minimize travel for infant and family and should enhance retention.
- The family will be given a reminder telephone call several days before the 2-4 month visit.
- Contact information will be verified and updated when the family comes to the 2-4 month EEG.
- If a family misses the 2-4 month EEG, then they will be contacted via telephone call within 3 days of the missed appointment. If there is no response, then an email will be sent after 5-7 days and/or a telephone call will be placed to the alternate phone number. The EEG will be rescheduled if at all possible.
- When the infant reaches 11 months, a letter will be mailed and/or emailed to the family, to remind them of the 12month telephone assessment. Families will be asked to contact the study coordinator to arrange a mutually convenient time for the 12-month telephone interview. If the family does not reply, the study coordinator will contact them via telephone and/or email to confirm an appointment for the follow-up assessment.
- In the event that an enrolled infant dies, the site's electronic medical record will be updated per local protocol. Many of the sites utilize an electronic medical record that automatically notifies a study team of a participant's death. The site study coordinators will verify that the patient is listed as living prior to extending an invitation for follow-up. If the patient is listed as deceased, the family will not be contacted.
- If a family withdraws from the study, the coordinators will attempt to document the reason for withdrawal so that issues can be identified and addressed.

Data Collection to Address Confounding: We will prospectively collect data for potential confounders to allow for the planned propensity scoring analysis, including:

- Term versus preterm at birth
- Confirmation of electrographic seizures versus diagnosis on clinical grounds alone
- Severity of seizures
- Etiology of seizures
- Number of seizure medications during the inpatient hospitalization
- Highest recorded phenobarbital level
- Abnormal neurological examination (consciousness, tone, or reflexes) at the time of discharge
- NICU length of stay
- Institution

Robust Analysis of Confounding Factors [DR-3]: Our plans to address analysis of confounding factors are addressed in the application's data analysis plan sections (see pages 9-12).
